## **Appendix 5**

### **Reasons for Exclusion from the Per-Protocol Population**

1. Select study inclusion criteria
  - Had more than 3 adequate prior DMTs (IC06)
  - No suboptimal response on the most recent adequately used DMT (IC07)
  - Suboptimal response while on last DMT that is less than 6 months (IC06)
  - Disease duration from first symptom of more than 12 years (Due to previous protocol versions has  $\leq$ 10 years as inclusion criteria, deviation code includes a mixture of deviations of  $>10$  years and  $>12$  years of duration. Thus for this criteria, program on clinical data will be used to identify patients with deviation.)
2. Select study exclusion criteria
  - History of PPMS, PRMS, or SPMS (EC01)
  - Previous treatment with natalizumab within 12 months prior to screening unless failure was due to confirmed, persistent ADAs (EC22)
  - Systemic corticosteroid therapy within 4 weeks prior to screening (EC24)

## **Appendix 6** **Statistical Analysis Plan for Shorter Infusion Substudy**

### **Background**

Ocrevus (ocrelizumab) is approved by the U.S. Food and Drug Administration (FDA) for the treatment of adults with primary progressive multiple sclerosis (PPMS) and relapsing multiple sclerosis (RMS). According to the currently approved U.S. label, ocrelizumab must be administered at a 600-mg dose through slow intravenous (IV) infusion. The first dose is given as two doses, separated by 14 days, and administered as two 300-mg infusions over the course of 2.5 hours, while subsequent doses are given as a single 600-mg infusion over 3.5 hours. This substudy will explore the effect of a shorter infusion of ocrelizumab on the rate and severity of infusion-related reactions (IRRs).

The most common safety events reported with ocrelizumab are IRRs. IRRs occur more frequently during the first infusion of the first dose. The majority of IRRs (>90% of patients reporting IRRs) were of mild to moderate intensity, and the intensity of IRRs decreased with subsequent dosing. The most frequently reported IRR symptoms during infusion in the ocrelizumab group were pruritus, rash, throat irritation, and flushing (33.0%, 29.2%, 29.8%, and 16.8% of patients with IRR, respectively) (see the Ocrelizumab Investigator's Brochure).

A Phase II, parallel-group, dose-finding trial (WA21493) evaluated ocrelizumab compared with placebo and Avonex (interferon- $\beta$ 1a) in patients with RRMS for up to 96 weeks. In this study, both the 600-mg and 1000-mg dose were administered over 4 cycles. After the first cycle, during which only the 600-mg dose was divided in half and given over a 15-day interval, subsequent cycles involved administration as a single, undivided dose. Doses were administered over approximately 240 minutes. The infusion schedule in this study shows that, both for the 600- and 1000-mg dose, approximately 400 mg of ocrelizumab were infused within 2 to 2.5 hours. However, in the remaining 1.5 to 2 hours of the infusion, only 200 mg remained to be infused for the lower dose, while in the 1000-mg dose, 600 mg were given within the same timeframe. Based on this infusion schedule, a dose/infusion rate/IRR relationship was not clearly observed.

The lack of dose/infusion rate/IRR relationship based on the current clinical data is supportive of the hypothesis that administration of ocrelizumab over a shorter infusion time should not pose a potential additional risk to patients in terms of increased risk of IRRs, but would help convenience of use and compliance for both patients and

healthcare practices. In addition, procedures are in place to further mitigate risk of IRR, such as a pre-treatment schedule and guidance around infusion adjustment, if required.

After the infusion, patients will be followed for safety, per the substudy schedule of activities, to monitor for any effects of the shorter administration.

### **Substudy Design**

This is an open-label, non-randomized substudy to MN30035 designed to evaluate the safety and tolerability of ocrelizumab infused over a shorter time period than the approved administration rate. Patients who complete their Week 72 ocrelizumab infusion and do not experience any serious IRR (see Section protocol 5.2.2 for seriousness criteria) throughout the main study will be eligible to enroll in this optional substudy and receive one additional shorter infusion of ocrelizumab at the Week 96 visit.

Premedication in the substudy will be administered per the main study methods (protocol Section 4.3.3). Ocrelizumab will then be administered as a single 600-mg dose at a shorter infusion rate (i.e., over the course of approximately 2 hours instead of 3.5 hours) than in the main study.

Ocrelizumab infusion rate will be slowed and/or stopped if a patient experiences a Grade 3 or higher IRR or other serious adverse event.

Patients who received ocrelizumab at a shorter infusion rate at the Week 96 visit will return for a substudy follow-up visit approximately 30 days after treatment.

The end of the treatment period in the substudy is defined as the date when the last patient in the substudy completes the substudy follow-up visit (Week 100).

### **Protocol Synopsis**

Refer to the main study protocol synopsis. For additional details, see the Schedule of Assessments in [Appendix A](#) and Rate of Shorter Infusion in [Appendix B](#).

### **Outcome Measures**

The primary objective of the substudy is to evaluate the rate and severity of IRRs of the ocrelizumab 600-mg infusion administered over the course of approximately 2 hours, instead of the currently approved duration of 3.5 hours, in patients with MS who have had prior treatment with ocrelizumab in study MN30035 (CHORDS), as measured by the rate and frequency of National Cancer Institute Common Terminology Criteria for Adverse Events, Version 4.0 (NCI CTCAE v4.0) Grade 3 and 4 IRRs. Specifically, the safety outcome measures are listed below.

- Rate and frequency of Grade 3 or 4 IRRs with onset on or after the shorter ocrelizumab infusion at Week 96 and at the substudy follow-up
- Changes in physical findings and vital signs with onset on or after the shorter ocrelizumab infusion at Week 96 and at the substudy follow-up

### **Determination of Sample Size**

This substudy will enroll approximately 100 patients from MN30035 who did not experience any serious IRR throughout the main study. Based on the sample size of 100 patients used for analysis, the 95% CIs for some assumed Grade 3 or 4 IRRs are provided in Table 1.

Table 1: Determination of Substudy Sample Size

| Number of Patients with Grade 3 or 4 IRRs | Grade 3 or 4 IRRs (%) (N=100) | 95% CIs for Grade 3 or 4 IRRs (%) |
|---|-------------------------------|-----------------------------------|
| 1   | 1.00                          | (0.03, 5.45)                      |
| 2   | 2.00                          | (0.24, 7.04)                      |
| 3   | 3.00                          | (0.62, 8.52)                      |
| 4   | 4.00                          | (1.10, 9.93)                      |
| 5   | 5.00                          | (1.64, 11.28)                     |
| 6   | 6.00                          | (2.23, 12.60)                     |
| 7   | 7.00                          | (2.86, 13.89)                     |

The 95% CIs for the IRR (%) are calculated based on the Clopper and Pearson method.

### **Analysis Timing**

The final analysis will be conducted when all patients enrolled in the substudy have received the shorter infusion and completed the 30-day safety follow-up assessments. Interim look for safety monitoring purpose can be conducted when deemed necessary.

### **Study Conduct**

#### **Randomization Issues**

Not applicable.

#### **Statistical Methods**

Safety analyses will include all patients who received any dose of study treatment through shorter infusion in the substudy.

Safety will be summarized using descriptive statistics. Continuous variables will be summarized using n (sample size), mean, standard deviation, median, minimum, and maximum. Frequency distributions (patient counts and associated percentages) will be used to summarize categorical variables. When applicable, 95% confidence intervals (CIs) will be provided for the mean and proportion. The Clopper and Pearson method will be used to calculate exact CIs for proportion when applicable.

### **Analysis of Study Conduct**

Patient disposition including the number of patients enrolled, discontinued, and completed the shorter infusion substudy will be summarized. Reasons for treatment and substudy discontinuations will also be summarized. Major protocol deviations that happened during the substudy period will also be summarized when applicable.

### **Demographics and Baseline Characteristics**

Patients' demographics, neurological examination, MS disease history (e.g., duration since MS first symptom, duration since MS diagnosis) at enrollment of the main study and previous DMTs before receiving any ocrelizumab in the main study will be summarized.

### **Safety Analyses**

Safety analyses of the substudy will include all patients who enrolled into the substudy and received >0 dose of the Week 96 shorter infusion.

### **Summary of IRRs**

The number and proportion of patients in the substudy who experienced Grade 3 or 4 IRRs with onset on or after the shorter infusion (including the safety follow-up period) will be summarized with the associated 95% exact confidence interval. The 2-sided 95% exact confidence interval will be calculated using the Clopper and Pearson method.

The incidence rate and the 2-sided 95% exact confidence interval will also be calculated for all Grade 1-4 IRRs.

The number and proportion of patients in the substudy who experienced local IRR and systemic IRR will also be summarized with 95% exact confidence interval.

Listings of Grade 3 or 4 IRRs, and IRRs that led to interruption of the shorter infusion or treatment withdrawal will be provided, if applicable, on the symptom of the IRR, CTCAE grade, infusion rate at the onset of IRR, action taken on ocrelizumab administration following the IRR, and the history of IRR events during the long infusion study period (e.g., highest CTCAE grade, frequency)

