5.3.3 Assessment of Severity of Adverse Events

The adverse event severity grading scale for the NCI CTCAE (v4.0) will be used for assessing adverse event severity. [Table 3](#) will be used for assessing severity for adverse events that are not specifically listed in the NCI CTCAE.

Table 3 Adverse Event Severity Grading Scale for Events Not Specifically Listed in NCI CTCAE

Grade	Severity
1	Mild; asymptomatic or mild symptoms; clinical or diagnostic observations only; or intervention not indicated
2	Moderate; minimal, local, or non-invasive intervention indicated; or limiting age-appropriate instrumental activities of daily living ^a
3	Severe or medically significant, but not immediately life-threatening; hospitalization or prolongation of hospitalization indicated; disabling; or limiting self-care activities of daily living ^{b,c}
4	Life-threatening consequences or urgent intervention indicated ^d
5	Death related to adverse event ^d

NCI CTCAE = National Cancer Institute Common Terminology Criteria for Adverse Events.

Note: Based on the most recent version of NCI CTCAE (v4.0), which can be found at: http://ctep.cancer.gov/protocolDevelopment/electronic_applications/ctc.htm

- ^a Instrumental activities of daily living refer to preparing meals, shopping for groceries or clothes, using the telephone, managing money, etc.
- ^b Examples of self-care activities of daily living include bathing, dressing and undressing, feeding oneself, using the toilet, and taking medications, as performed by patients who are not bedridden.
- ^c If an event is assessed as a "significant medical event," it must be reported as a serious adverse event (see Section 5.4.2 for reporting instructions), per the definition of serious adverse event in Section 5.2.2.
- ^d Grade 4 and 5 events must be reported as serious adverse events (see Section 5.4.2 for reporting instructions), per the definition of serious adverse event in Section 5.2.2.

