5.3.5.8 Deaths

All deaths that occur during the protocol-specified, adverse event, reporting period (see Section 5.3.1), regardless of relationship to study drug, must be recorded on the Adverse Event eCRF and immediately reported to the Sponsor (see Section 5.4.2). This includes death attributed to progression of RRMS.

Death should be considered an outcome and not a distinct event. The event or condition that caused or contributed to the fatal outcome should be recorded as the single medical concept on the Adverse Event eCRF. Generally, only one such event should be reported. The term "**sudden death**" should be used only for the occurrence of an abrupt and unexpected death due to presumed cardiac causes in a patient with or without preexisting heart disease, within 1 hour after the onset of acute symptoms or, in the case of an unwitnessed death, within 24 hours after the patient was last seen alive and stable. If the cause of death is unknown and cannot be ascertained at the time of reporting, "**unexplained death**" should be recorded on the Adverse Event eCRF. If the cause of death later becomes available (e.g., after autopsy), "unexplained death" should be replaced by the established cause of death.

If the death is attributed to progression of RRMS, "RRMS progression" should be recorded on the Adverse Event eCRF.

Ocrelizumab—Genentech, Inc.
53/ Protocol MN30035, Version 5

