Appendix 2 ***Optional Shorter Infusion Substudy (cont.)***

OBJECTIVES

The primary objective of this study is to evaluate the rate and severity of infusion-related reactions (IRRs) of the ocrelizumab 600-mg infusion administered over the course of 2 hours, instead of the currently approved duration of 3.5 hours, in patients with MS who have had prior treatment with ocrelizumab in MN30035 (CHORDS), as measured by the rate and frequency of National Cancer Institute Common Terminology Criteria for Adverse Events, Version 4.0 (NCI CTCAE v4.0) Grade 3 and 4 IRRs.

STUDY DESIGN

This is an open-label, non-randomized substudy to MN30035 designed to evaluate the safety and tolerability of ocrelizumab infused over a shorter time period than the approved administration rate. Patients who complete their Week 72 ocrelizumab infusion and do not experience any serious IRR (see Section 5.2.2 for seriousness criteria) throughout the main study will be eligible to enroll in this optional substudy and receive one additional shorter infusion of ocrelizumab at the Week 96 visit.

Premedication in the substudy will be administered per the main study methods (Section 4.3.3). Ocrelizumab will then be administered as a single 600-mg dose at a shorter infusion rate (i.e., over the course of approximately 2 hours instead of 3.5 hours) than in the main study.

Ocrelizumab infusion rate will be slowed and/or stopped if a patient experiences a Grade 3 or higher IRR or other serious adverse event.

Patients who received ocrelizumab at a shorter infusion rate at the Week 96 visit will return for a substudy follow-up visit approximately 30 days after treatment.

The end of the treatment period in the substudy is defined as the date when the last patient in the substudy completes the substudy follow-up visit (Week 100).

Planned Total Sample Size

This substudy will enroll approximately 100 patients from MN30035 who did not experience any serious IRR throughout the main study.

OUTCOME MEASURES

Safety Outcome Measures

- *Rate and frequency of Grade 3 or 4 IRRs with onset on or after the shorter ocrelizumab infusion at Week 96 and at the substudy follow-up*
- *Changes in physical findings and vital signs with onset on or after the shorter ocrelizumab infusion at Week 96 and at the substudy follow-up*

Ocrelizumab—Genentech, Inc.
80/ Protocol MN30035, Version 5

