### **Adverse Events**

All adverse events occurring on or after the shorter infusion (including the safety follow-up period) will be coded, summarized by NCI CTCAE v4.0 grade, and tabulated by body system and Preferred Term for individual adverse events within each body system. All adverse events, Grade 3 to 5 adverse events, serious adverse events, adverse events leading to treatment discontinuation, time to withdrawal from the study due to an adverse event, adverse events leading to infusion adjustment, and treatment-related adverse events will be summarized. In addition, all serious adverse events and deaths will be listed if applicable.

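### The substudy's two graded infusion-reaction rates stop at Grade 4, so under worst-grade classification a fatal (Grade 5) reaction would be counted in neither (minor)

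*SAP*

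**What the plan says.** Protocol Appendix 2 gives the substudy's first safety outcome as "Rate and frequency of Grade 3 or 4 IRRs with onset on or after the shorter ocrelizumab infusion at Week 96" and at the follow-up visit. SAP Appendix 6 repeats this under Outcome Measures. The precision tables (Table 2 in Protocol Appendix 2, Table 1 in SAP Appendix 6) carry the same Grade 3 or 4 label.

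Under Summary of IRRs, the SAP will report "The number and proportion of patients in the substudy who experienced Grade 3 or 4 IRRs with onset on or after the shorter infusion" with a Clopper-Pearson interval. It then adds: "The incidence rate and the 2-sided 95% exact confidence interval will also be calculated for all Grade 1-4 IRRs". One of the listings in that section is also limited to Grade 3 or 4.

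Other parts of the plan have no such ceiling:

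- Substudy Design, in the same appendix: "Ocrelizumab infusion rate will be slowed and/or stopped if a patient experiences a Grade 3 or higher IRR".
- Adverse Events, in the same appendix, summarises "All adverse events, Grade 3 to 5 adverse events, serious adverse events, adverse events leading to treatment discontinuation", among others.
- Protocol Section 5.3.3, Table 3, defines Grade 5 as "Death related to adverse event".
- Protocol Section 5.3.5.8: "Death should be considered an outcome and not a distinct event". The causal event is what goes on the adverse event form.

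**The concern.** The substudy asks whether infusing over about 2 hours instead of 3.5 raises the rate or severity of IRRs. A severity rate used for that purpose should be open at the top, so that a worse outcome never lowers it. Here both graded rates are closed at Grade 4. Because death is recorded as the outcome of the causal event, a reaction that ends in death is a Grade 5 IRR, not a separate death record. Taken literally, it meets neither grade range.

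No reason for the ceiling is given. The same appendix uses Grade 3 or higher and Grade 3 to 5, so the cap looks like a drafting slip. At stake is whether the substudy's main safety figure is right in the one case where it matters most.

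**Working it through.** **Inputs.** n = 100 (SAP Appendix 6, Determination of Sample Size; enrolment is approximate). Intervals are two-sided 95% Clopper-Pearson (Summary of IRRs). The denominator is everyone enrolled in the substudy who received more than zero dose of the shorter infusion (SAP Appendix 6, Safety Analyses), so a patient who dies stays in it.

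**Formulas.** For x patients with the event:
- lower limit = 2.5% quantile of Beta(x, n − x + 1), or 0 when x = 0
- upper limit = 97.5% quantile of Beta(x + 1, n − x)
- for x = 0, the upper limit reduces to 1 − 0.025^(1/n)

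**Reproducing the plan's table.** With n = 100 and x = 1 to 7, these give (0.03, 5.45), (0.24, 7.04), (0.62, 8.52), (1.10, 9.93), (1.64, 11.28), (2.23, 12.60) and (2.86, 13.89). All seven rows agree with the table to two decimals. The table has no row for x = 0. There the upper limit is 1 − 0.025^(1/100) = 3.62%.

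**Effect of the cap on the primary rate, under worst-grade classification:**

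| Reactions among 100 patients | As written (Grade 3 or 4) | Counting Grade 3 to 5 |
|---|---|---|
| One fatal IRR, no other | 0% (0 to 3.62) | 1% (0.03 to 5.45) |
| One Grade 3 or 4 IRR and one fatal | 1% (0.03 to 5.45) | 2% (0.24 to 7.04) |
| Two Grade 3 or 4 IRRs and one fatal | 2% (0.24 to 7.04) | 3% (0.62 to 8.52) |

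In the first row the Grade 1-4 rate is also 0/100, so both graded rates show no reaction. In general, each fatal IRR lowers each count by one.

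**The classification assumption.** SAP Section 4.7.2 uses the highest grade per patient for main-study IRRs, but Appendix 6 does not say so for the substudy. Protocol Section 5.3.5.4 records both the initial and the most extreme severity of a persistent event. If an initial grade were counted instead, a reaction that began at Grade 3 or 4 and became fatal would enter both rates. One that began at Grade 1 or 2 would enter only the Grade 1-4 rate. Nothing in the SAP says initial grades are used.

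**How likely.** The documents give no rate of fatal IRR. As an illustration only, the chance of at least one among 100 patients is 1 − (1 − p)^100. An assumed p of 1 in 10,000 gives 1.0%, and 1 in 1,000 gives 9.5%.

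**The case against.** A reader might infer that a fatal reaction would disappear from the IRR results, or show up only in general adverse event tables and the death listing. The documents do not support that:

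- Summary of IRRs also reports the proportions with local and with systemic IRRs, with exact intervals and no grade limit. Protocol Section 5.3.5.1 makes the split exhaustive: whatever is not a skin reaction in one place is systemic. A fatal IRR would enter one of these proportions.
- The listing sentence there also covers IRRs that led to interruption of the infusion or to withdrawal, whatever their grade. A reaction that interrupted the infusion would be listed with its grade; a delayed one might not be.
- The Adverse Events section tabulates events by grade and Preferred Term and covers Grade 3 to 5 and serious events. It adds: "In addition, all serious adverse events and deaths will be listed if applicable".

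A reader might also infer that the cap could make the shorter infusion pass a safety test. The substudy is descriptive, and no hypothesis test, threshold or decision rule is attached to the rate.

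Two further objections have weight. Table 3 in Protocol Section 5.3.3 applies to events not specifically listed in the CTCAE, so it need not govern IRRs. The Grade 3 to 5 summary shows that Grade 5 is in use in the substudy anyway. The event is also improbable: patients with a serious IRR in the main study are excluded, and no IRR is among the causes of death named for the controlled Phase III periods in Protocol Section 1.2.1.2.

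These objections limit the weight of the point. They do not change what the two graded rates count.

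**Conclusion.** The point holds as a minor defect of definition. As written, and assuming worst-grade classification, a fatal IRR is in neither graded rate and not in the Grade 3 or 4 listing. The error is one patient in about 100 for each such event: at the extreme, 0% (0 to 3.62%) where 1% (0.03 to 5.45%) is correct.

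The expected effect is small because the event is unlikely and would be visible in several other planned outputs. It is still worth correcting, because the stated rule gives the wrong rate in the worst case and departs from the grade ranges used elsewhere in the same appendix.

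**What to change.** In SAP Appendix 6, define the primary rate and its listing as Grade 3 or higher (3 to 5), and the supporting rate as any grade (1 to 5). This affects Outcome Measures, the Table 1 heading and Summary of IRRs. A sentence stating that each patient is classified by highest IRR grade, as in SAP Section 4.7.2, would remove the assumption made above.

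Align the objective, outcome measures and Table 2 heading in Protocol Appendix 2 at the next amendment. Section 9.6 generally requires ethics approval before protocol changes take effect, and this point alone does not warrant an amendment; the SAP wording is enough to make the analysis correct.

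The cost is a few words. Sample size and data collection are unchanged. The table's intervals also stand, since they depend only on the count and n.
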